### 5.2 PPS

This comprises all randomized subjects who are included in the FAS, and to whom the below conditions do not apply. This set will be fixed before key break, on the basis of subject handling criteria that are prepared separately from the present document.

- Not meeting the inclusion criteria, and/or violating the exclusion criteria, in the protocol
- Insufficient compliance in study drug use.
- Violation of restrictions on concomitant treatment.

### 5.3 Safety-analysis set

This set comprises all randomized subjects to whom the study drug has been administered at least once. Analysis of this set will be performed with subjects actually administered the study drug, rather than allocated group.

## 6. Issues with statistical analysis, and data handling

### 6.1 Reporting of analysis results

The numbers of subjects, arithmetic means, standard deviations, minima, medians, and maxima will in principle be calculated as summary statistics for the endpoints measured as continuous data. Items observed as discrete values will be summarized as the number and proportion of subjects in each category. The software used for statistical analyses in this study will be SAS, Version 9.4.

### 6.2 Statistical tests

The level of significance for the statistical tests will be 0.05 (two-sided), unless stated otherwise. The

primary endpoint in this study will be only change in CDRS-R total score from baseline, and no analyses will be performed taking into consideration multiplicity concerning multiple items and multiple time-points.

### 6.3 Assessments, observations and tests: Permitted timing and handling in statistical analyses

In principle, data obtained at the time-points shown in the case report forms, and collected in accordance with the performance schedule shown in the study protocol, will be used for the statistical analysis. In the case of data reported at the discontinuation visit, the time-points for use in analyses will be determined on the basis of the permitted ranges in the performance schedule. If there is duplication by data obtained at the scheduled visits and data obtained at the discontinuation tests, the data obtained closest to the scheduled date will be used. If this does not eliminate duplication, data from the scheduled visit will be used. Unscheduled visits will not be included in the time-points for analysis. For the permitted ranges for the observation, test, and evaluation time-points shown in the study protocol, refer to Appendix 2.

For the final evaluation, data obtained at week 7 or at discontinuation of the treatment or tapering period are used, except for CDRS-R and CGI-S scores, for which those obtained at week 6 or at discontinuation of the treatment period are used. However, if none of the above data are available, the latest data among reported data collected at scheduled visits are used for the final evaluation.

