### 6.4 Handling of missing data

In principle, missing data will not be imputed. If missing data for CDRS-R total scores 6 weeks after initial administration are nevertheless imputed for the secondary efficacy analyses, this will be performed by the last observation carried forward (LOCF) method, baseline observation carried forward (BOCF) method, and modified BOCF method.

If missing data imputation is performed by the LOCF method, the measurements used as substitutes will be those obtained at the latest scheduled evaluation time-points (Visits 3, 4, 5, 6 and 7) before the missing-data time-points.

If missing data imputation is performed by the BOCF method, the baseline data will be used as substitutes.

The modified BOCF method is defined as follows:

- With subjects withdrawn from the study due to adverse events and/or insufficient efficacy, imputation will be by the BOCF method.
- With subjects withdrawn from the study for any reason other than the above, imputation will be by the LOCF method.

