### 9.1.2 Secondary analysis of primary endpoint

1) Analysis of the PPS by the MMRM method

Change in CDRS-R total score will be analyzed with the PPS, in the same manner as the primary analysis.

2) Analysis of change at week 6 of administration (analysis of covariance)

A) An analysis of covariance will be performed with change in CDRS-R total score from baseline to week 6 of administration as the response variable; treatment group as the fixed effect; and baseline CDRS-R total score, and age (<12, ≥12) as covariates. The estimated inter-group difference and 95% confidence interval, and p-value, will thus be calculated. If the CDRS-R total score at week 6 of administration is not available, the missing data will be imputed by the LOCF method.

B) On the basis of missing data imputation by the BOCF method, analysis of covariance will be performed in the same manner as above.

C) Likewise, analysis of covariance will be performed on the basis of missing data imputation by the modified BOCF method.

3) Supplemental analysis of missing data imputation methods:

With respect to change in CDRS-R total score, with multiple imputation with missing at random hypothesized, solely in the case of the duloxetine group the k-multiple of the inter-group difference ( $k = 0.1, 0.2, \dots$ ) for the treatment-group primary effect in the primary analysis MMRM method will be subtracted from the data obtained by missing data imputation, and analysis will be performed in a similar manner to the primary analysis. Despite differences in the time from baseline to the point at which data are missing, the subtracted values will be set the same. In the case of multiple imputation, taking the imputation to be performed 100 times, the seed value is set at 3,631. With respect to the analysis results (adjusted mean inter-group difference and standard error) with

imputation performed this number of times, these will be integrated as single results using proc mianalyze.

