### 9.2.1 Analysis of secondary efficacy endpoints

#### 1) Analysis of response rate and remission rate

For each of the indices defined below, the number of responders (number of subjects showing remission) and response rate (remission rate) will be obtained for each treatment group, at weeks 1 to 3, 5, and 6 of administration, and at the final evaluation (week 6 of administration, or at discontinuation of the treatment period), and the Cochran-Mantel-Haenszel test, with stratification by the allocation factor age (<12, ≥12), will be used to compare the duloxetine and placebo groups. In addition, the inter-group difference in response rate (remission rate), and the 95% confidence interval, will be calculated.

Index	Definition
30% response	Reduction of 30% or more in CDRS-R total score compared with baseline
50% response	Reduction of 50% or more in CDRS-R total score compared with baseline
Remission	CDRS-R total score of 28 or less

An analysis with withdrawn subjects taken to be non-responders (non-remission subjects) will also be performed.

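### When SAP 6.3 removes a discontinuation CDRS-R because it is no nearer the scheduled date than an earlier scheduled rating in the same window, LOCF carries that earlier score and not the last observation

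*SAP*

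**What the plan says.** Four rules in the SAP bear on a subject who stops during the treatment period.

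- **Assignment to a visit (SAP 6.3).** For a rating reported at the discontinuation visit, "the time-points for use in analyses will be determined on the basis of the permitted ranges in the performance schedule".
- **Duplicates (SAP 6.3).** When a scheduled and a discontinuation rating land on the same time-point, "the data obtained closest to the scheduled date will be used". For equal distances: "If this does not eliminate duplication, data from the scheduled visit will be used".
- **LOCF source (SAP 6.4).** The substitute values are "those obtained at the latest scheduled evaluation time-points (Visits 3, 4, 5, 6 and 7) before the missing-data time-points". The method is applied in the secondary ANCOVA of SAP 9.1.2: "If the CDRS-R total score at week 6 of administration is not available, the missing data will be imputed by the LOCF method". It is also used in modified BOCF for subjects withdrawn for reasons other than adverse events or insufficient efficacy.
- **Final evaluation (SAP 6.3).** This is a separate rule for CDRS-R and CGI-S scores, "for which those obtained at week 6 or at discontinuation of the treatment period are used". SAP 9.2.1 applies it to the 30% and 50% response rates and to remission.

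SAP Appendix 2 gives Visits 3 to 7 a range of ±3 days and places the discontinuation assessment 0 to 3 days after the last treatment-period dose. CDRS-R is not scheduled at Visit 6 (protocol 7.5.1 and the schedules). The LOCF provisions in protocol 8.4 and 8.10.3 do not limit the carried value to scheduled time-points.

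**The concern.** Nearest-date selection is an ordinary way to fill a visit slot. The difficulty comes when its result feeds LOCF. A subject seen on the nominal day who stops one to three days later has two ratings in one window. The scheduled one is kept, and nothing in SAP 6.4 restores the later one. The analysis called LOCF then carries a score that is not the last observed during the treatment period.

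The dropped rating is the one taken when treatment ended. Protocol 4.5 lists aggravation through insufficient efficacy among the reasons for stopping, so that rating can differ systematically from the visit before it. The SAP also treats the same rating as valid elsewhere, because the final evaluation uses it. Two planned analyses can therefore describe one subject's end state by different scores, with no reason given.

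**Working it through.** **1. The plan's own figures.** The documents attach no number to the duplicate rule, but the sample-size inputs set the scale. Inputs (protocol 8.2, SAP 4.3): difference 5.9, SD 12.0, two-sided 0.05, power 80%, drop-out 10%.

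- The normal approximation gives 65 per group. The exact noncentral t gives power 0.7944 at 65 and 0.8005 at 66, so 66 per group is reproduced.
- 66 / 0.90 = 73.3, rounded up to 74 per group, 148 in total. This point does not change it.

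**2. Windows in which a duplicate can arise.** Visit 3: days 4–10. Visit 4: days 11–17. Visit 5: days 18–24. Visit 7: days 32–38. The Visit 6 window (days 25–31) has no scheduled CDRS-R, so no pair occurs there.

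**3. All whole-day pairs in one ±3-day window.** Let v be the scheduled rating's offset from the nominal day and d the later discontinuation rating's offset (d > v). SAP 6.3 keeps the later rating only if |d| < |v|.

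| v | Possible later d | Later rating discarded |
|---|---|---|
| −3 | 6 | 1 (tie) |
| −2 | 5 | 2 (1 tie) |
| −1 | 4 | 3 (1 tie) |
| 0 | 3 | 3 |
| +1 | 2 | 2 |
| +2 | 1 | 1 |
| +3 | 0 | 0 |
| Total | 21 | 12 (3 ties) |

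The later rating is discarded in 12/21 = 57% of pairs: 6 of 6 when the scheduled visit was on or after its nominal day, and 6 of 15 when it was early. This counts possible day combinations. It does not estimate how often they will occur.

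- Discarded: Visit 5 on day 21, discontinuation rating on day 23. Day 21 is kept, and LOCF carries it.
- Kept: Visit 5 on day 18, discontinuation rating on day 22. The distances are 3 and 1 days, so day 22 is kept and LOCF does carry the last observation.

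**4. One subject under two rules (illustrative scores).** Baseline 60, Visit 7 on day 35 scores 38, discontinuation on day 37 scores 48.

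- LOCF ANCOVA: 38 − 60 = −22, a fall of 22/60 = 36.7%.
- Final evaluation: 48 − 60 = −12, a fall of 12/60 = 20%, so not a 30% responder.

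**5. How many ratings.** No offset in the table loses more than 3 days per window, and a visit on its nominal day reaches that maximum. Over four windows this is 4 × 3 = 12 of 42 treatment days, or 28.6%. Drop-outs: 0.10 × 148 = 14.8, about 15. If discontinuation ratings are spread evenly over the days and every drop-out has one, 0.286 × 15 = 4.3 ratings are lost.

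**6. Effect on the LOCF difference.** Assume one arm loses 2 more ratings than the other and each lost rating differs by g points from the one kept. The shift is 2 × g / 74.

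- g = 3: 6/74 = 0.08 points, or 1.4% of 5.9.
- g = 10: 20/74 = 0.27 points, or 4.6% of 5.9.

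**The case against.** The rule is explicit, leaves the analyst no discretion, and is fixed before the key break. SAP 6.4 states what its LOCF carries, so part of the complaint concerns a label. The LOCF ANCOVA is secondary. Other planned analyses cover much of the ground: BOCF, modified BOCF (which gives baseline values to subjects withdrawn for adverse events or insufficient efficacy), the tipping-point analysis, and a response analysis that counts withdrawn subjects as non-responders. Different drop-out rules are expected to give different answers. The discontinuation rating may also follow the last treatment-period dose by up to 3 days, and protocol 7.5.1 asks for it only if possible.

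Most of this stands and limits the weight of the point. It does not explain why a rating accepted for the final evaluation should be unavailable to LOCF.

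Three stronger readings are tempting, and the documents do not support them.

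- **That the discontinuation rating is always lost, or that SAP 6.4 shuts out all such ratings.** It is kept in 9 of the 21 pairs. One that is alone in its window becomes that time-point's value under SAP 6.3 and can be carried forward. The listing of Visit 6 as a LOCF source fits this, since no CDRS-R is scheduled there.
- **That the primary MMRM is blind to outcome-related drop-out and its visit rule must be overridden.** The duplicate rule does select the MMRM's by-visit values, but only some same-window ratings are lost. Replacing the nearer scheduled rating with one that may follow the last treatment-period dose is a debatable trade-off, and no effect on the primary result has been shown.
- **That the shift is about half a point.** This needs a 20-point gap between ratings 1 to 3 days apart (2 × 20 / 74 = 0.54). That gap is 20/12.0 = 1.7 times the SD assumed for the whole six-week change, and nothing in the documents supports it.

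**Conclusion.** The point holds for a defined set of subjects: those whose discontinuation CDRS-R shares a Visit 3, 4, 5 or 7 window with an earlier scheduled rating and is no nearer the scheduled date. For them, SAP 6.3 and 6.4 together make LOCF carry a score other than the last one observed, and the LOCF ANCOVA then disagrees with the final-evaluation response and remission analysis about the end state. Modified BOCF is affected only for withdrawals that it handles by LOCF.

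The consequence is small: about 4 ratings at most, and 0.08 to 0.27 points on a secondary comparison. These figures rest on the planned 10% drop-out, even spread of discontinuations, a rating from every drop-out, an imbalance of 2, and a gap of 3 to 10 points. Only the first of these is in the documents. The direction is unknown, because it depends on which arm loses more ratings and whether they were worse or better. No bias for or against duloxetine can be claimed. It is worth correcting because the rule yields a wrong value for the method it names and the remedy is trivial.

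**What to change.** In SAP 6.4, define the LOCF value as the last CDRS-R total score obtained after the start of study drug, up to and including the treatment-period discontinuation rating, even where SAP 6.3 has removed that rating as a duplicate for the by-visit analysis. State that the same value serves the LOCF part of modified BOCF. This matches the final-evaluation rule already in SAP 6.3. Leave the nearest-date rule unchanged for the by-visit MMRM.

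The cost is a sentence or two of SAP wording, settled before the key break, and a small change to the derivation program. No new data are needed, and the sample size and primary analysis are unaffected. The downside is that the carried rating may fall up to 3 days after the last treatment-period dose, which the SAP already accepts for the final evaluation.

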- Tapering period: In order to minimize the occurrence of adverse events due to discontinuation of administration, a 1-week tapering period is set for subjects who complete the treatment period, or who withdraw from it during the second week or later, and during this time duloxetine or placebo will be administered orally, once daily after breakfast, with double-blinding. If the duloxetine dose at discontinuation or completion of the treatment period is 60 mg/day, 40 mg/day will be administered for the first 3 days of the 1-week tapering period, and 20 mg/day will be administered for the remaining 4 days. On the other hand, if the dose at discontinuation or completion is 40 mg/day, 20 mg/day will be administered for the entire week (for details about the tapering method at discontinuation of the treatment period, refer to Section 5.2).
- Follow-up period: No study drugs will be administered during the 1-week follow-up period. This period is set to enable evaluation of any adverse events during the week after completion of study drug administration, irrespective of whether or not the dose was tapered. If administration is discontinued during the treatment period, and there is then no administration during the tapering

period, a 1-week run-out period will be set after administration discontinuation.

The study design is shown in Fig. 3-1. The study schedule is shown in Appendix 1.

Fig. 3-1. Schematic diagram of study schedule

a Visit 6 is a visit that can be made to the hospital in connection with dose increase, decrease, etc.

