- 3) Discontinuation during week 3 to 6 of treatment period: If the duloxetine dose at administration discontinuation is 60 mg/day, discontinue after tapering-period administration of the study drug, at 40 mg/day for 3 days, and 20 mg/day for 4 days.

If the duloxetine dose at administration discontinuation is 40 mg/day, discontinue after tapering-period administration of the study drug at 20 mg/day for 7 days.

However, tapered administration may be omitted if serious adverse drug reactions occur, there are safety-related problems, or the subject or his/her legal representative refuses the tapered administration.

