7.6.6 Laboratory tests

7.6.6.1 Laboratory test items

At Visits 1, 5, 8 and 9, or at discontinuation of the treatment period or tapering period, blood samples will be collected for laboratory tests, the volumes being 2 mL for hematology tests, and 8 and 5 mL for blood chemistry tests, at Visit 1 and other visits, respectively; and urine samples will also be collected. The samples will then be sent to the clinical laboratory facility specified in Section 7.6.6.2. Details of the collection, handling, storage, and shipment of samples are stipulated in a separate document.

The principal investigator or sub-investigator will judge whether any abnormal change from baseline (Visit 1) is clinically significant (see Section 7.6.7.7) and will record any changes judged to be clinically significant as adverse events. The sample collection dates will be recorded in the CRF for each sample type (blood or urine).

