Appendix 2: Management of abnormal hepatic function test results, and discontinuation criteria

In order to ensure subjects' safety, as well as to evaluate the causes of any hepatic dysfunction found, management on the basis of abnormal hepatic function test results, and the discontinuation criteria, are defined, on the basis of the FDA's July 2009 guidance (Guidance for Industry Drug-Induced Liver Injury: Premarketing Clinical Evaluation).

(1) Hepatic dysfunction criteria

The principal investigator or sub-investigator confirms whether or not the subject's laboratory test results meet any of the following criteria:

- a. AST and/or ALT >5 times the upper limit of normal (ULN) .
- b. AST and/or ALT >3 times the upper limit of normal (ULN) , and total bilirubin >2 times the upper limit of normal (ULN) .
- c. AST and/or ALT >3 times the upper limit of normal (ULN) , and signs and/or symptoms consistent with hepatitis or hypersensitivity (e.g. fatigue, nausea, vomiting, right upper abdominal pain or tenderness, jaundice, fever, rash, eosinophil increase by more than 5%).

(2) Principal investigator's actions

If one or more of the above hepatic dysfunction criteria is met, the principal investigator or sub-investigator will act as follows:

- Immediately ensure that the subject stops taking the study drug.
- If possible, have the subject visit hospital within 72 hours after the abnormalities are first found, to repeat the hepatic function tests for a supplementary evaluation of hepatic function.
- Until the hepatic function test result (ALT, AST, ALP, and total bilirubin) abnormalities cease, stabilize, or return to within the reference range or to the baseline, the subject's progression is observed two to three times per week, if possible.
- Report to the sponsor using the hepatic dysfunction follow-up assessment form, within 72 hours after the relevant abnormalities coming to the principal investigator's attention.
- Look into the option of consulting a hepatologist or other specialist.
- Look into the option of performing hepatic imaging, such as ultrasonography, magnetic resonance imaging, or computed tomography.
- Report all events that meet criterion b (above) as serious adverse events.

(3) Follow-up assessment

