If one or more of the above hepatic dysfunction criteria is met, items including the following will be assessed at the time of the follow-up assessment visit, and the results will be entered in the hepatic dysfunction follow-up assessment form:

- Clinical symptom.

- Alcohol intake.
- Risk factors for nonalcoholic steatohepatitis (NASH) (e.g. diabetes, obesity, and hypertriglyceridemia).
- Autoimmune hepatitis and cholangitis.
- Wilson's disease.
- Laboratory tests:
 - The following serum tests relating to viral hepatitis:
 - > Hepatitis A IgM antibody
 - > Hepatitis B surface antigen and hepatitis B core antibody
 - > Hepatitis C RNA
 - > Hepatitis E IgA antibody
 - > Cytomegalovirus IgM antibody
 - > Epstein-Barr virus capsid antigen IgM antibody
 - In the case of subjects with total bilirubin >1.5 times the upper limit of the reference values, conjugated bilirubin will be measured.
 - Blood cell measurement will be carried out, including leukocyte fractions.

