## 10.3 Analysis of laboratory test results

The below laboratory test results will be analyzed. The time-points for evaluation of laboratory test results are taken to be the screening period (baseline), weeks 3 and 6 after administration initiation, and the final evaluation time (week 7, or at discontinuation of the treatment period or tapering period). However, for HbA1c, TSH, FT3 and FT4, evaluation is solely during the screening period.

Classification	Parameter
Hematology tests	Leukocyte count, erythrocyte count, hemoglobin, hematocrit, leukocyte fractions (eosinophils, basophils, neutrophils, monocytes, lymphocytes), platelet count
Blood chemistry	AST, ALT, LDH, $\gamma$ -GTP, ALP, creatine kinase, total bilirubin, total protein, blood

Classification	Parameter
	urea nitrogen, serum creatinine, uric acid, total cholesterol, triglycerides, Na, K, Cl, Ca, blood glucose, HbA1c, TSH, FT3, FT4
Urinalysis (qualitative)	Urinary protein, urinary glucose, urobilinogen, urinary occult blood

- 1) With respect to laboratory test results obtained as continuous values, summary statistics of observed values at each evaluation time-point, and changes from baseline, will be calculated for each treatment group.
- 2) With respect to urinalysis parameters obtained as qualitative values, the number and proportion of subjects in each category at each evaluation time-point will be determined for each treatment group.
- 3) As evaluation of liver function, the numbers and proportions of subjects meeting the following criteria at each evaluation time-point, and the numbers and proportions meeting these criteria at least one evaluation time-point after administration initiation, will be determined for each treatment group:
  - AST >5 times the upper limit of the reference values.
  - ALT >5 times the upper limit of the reference values.
  - AST or ALT >3 times the upper limit of the reference values, and total bilirubin >2 times the upper limit of the reference values
  - AST >3 times the upper limit of the reference values.
  - ALT >3 times the upper limit of the reference values.

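### Liver threshold counts in SAP 10.3 leave out off-schedule hepatic repeat tests, so a limit first crossed at such a repeat is not tabulated unless it is recorded as the discontinuation test

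*SAP*

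**What the plan says.** SAP 6.3 sets the general rule: "Unscheduled visits will not be included in the time-points for analysis". It makes no exception for safety data, and its fallback for the final evaluation is also limited to scheduled visits.

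SAP 10.3 gives the post-dose laboratory time-points as "weeks 3 and 6 after administration initiation, and the final evaluation time (week 7, or at discontinuation of the treatment period or tapering period"). Item 3 of that section then asks for by-time-point liver counts and for the "numbers and proportions meeting these criteria at least one evaluation time-point after administration initiation". These are called the ever-met rows below. The limits are AST >5x ULN, ALT >5x, AST or ALT >3x with total bilirubin >2x, AST >3x and ALT >3x.

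Protocol 7.6.6.1 fixes the planned draws: "At Visits 1, 5, 8 and 9, or at discontinuation of the treatment period or tapering period, blood samples will be collected". Visit 10 has none (Protocol Appendix 1).

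Protocol Appendix 2 defines three hepatic criteria: (a) AST or ALT >5x; (b) AST or ALT >3x with bilirubin >2x; (c) AST or ALT >3x with signs or symptoms. When one is met, study drug stops and the site is told: "If possible, have the subject visit hospital within 72 hours after the abnormalities are first found, to repeat the hepatic function tests". Observation two or three times a week follows, where possible, until the values settle. For the follow-up assessment, "the results will be entered in the hepatic dysfunction follow-up assessment form".

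**The concern.** The ever-met rows use the limits of criteria a and b, plus the single-enzyme >3x limits. Once a criterion is met the protocol intensifies testing, and the SAP rule removes most of that extra testing from the count. A subject whose enzymes or bilirubin rise further after the first abnormal sample can be left out of the higher or combined row.

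The error runs one way: dropping post-dose results can lower an ever-met count but cannot raise it. The combined enzyme and bilirubin row is the one where a change from one case to none matters most to a reader of the safety tables. A report could list a serious adverse event for criterion b while the matching liver row shows zero.

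**Working it through.** No figure in the plan is at issue, so the check sets the rules side by side.

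**1. Planned post-dose chemistry.** A completer has draws at Visits 5, 8 and 9, nominally days 21, 42 and 49: three results.

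**2. Which repeats are counted.** A crossing at one of those visits is counted. So is a repeat recorded as the discontinuation test, whose window is 0 to +3 days from the last dose of the period. That window can overlap the 72-hour target, so the first repeat may qualify. Later repeats fall outside it.

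**3. Where the count fails.**
- *First found at Visit 9.* This is the last planned draw. A subject who has finished the taper has no discontinuation test to take in the repeat. The repeat may fall inside Visit 9's own 0 to +3 day window, but it is still an additional, unscheduled visit.
- *Drug stopped for a liver criterion, taper omitted.* Protocol 5.2 allows this: "tapered administration may be omitted if serious adverse drug reactions occur, there are safety-related problems". Protocol 3.1 then provides that "a 1-week run-out period will be set after administration discontinuation". No planned draw follows the discontinuation test, so later repeats are uncounted.
- *Trigger sample itself unscheduled.* The week 3 window is 21 ± 3 = days 18 to 24 (7 days). The week 6 window is days 39 to 43 (5 days). Of days 1 to 43, 43 − (7 + 5) = 31 lie outside both. A result there enters only through the discontinuation or final evaluation. If no counted sample meets the limit, every liver row is at risk.

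**4. Two worked cases at Visit 9.**

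| | Visit 9 | 72-hour repeat | In the liver rows | Missing from |
|---|---|---|---|---|
| Case 1 | ALT >5x (criterion a) | bilirubin >2x for the first time, ALT still >3x | ALT >3x, ALT >5x | combined row |
| Case 2 | ALT between 3x and 5x with symptoms (criterion c) | ALT >5x for the first time | ALT >3x | ALT >5x row |

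Case 1 is still a serious adverse event (Protocol 7.6.7.8.1 and Appendix 2). Case 2 has no automatic serious-event rule. It is recorded as an adverse event (Protocol 7.6.7.7), but SAP 10.1 tabulates by MedDRA term without multiples of ULN. The only SMQs it lists are suicide/self-injury and hostility/aggression.

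**5. Repeat results per affected subject.** Assume that each observation includes a test and that the abnormality lasts 1 to 3 weeks; neither is stated.
- Low: 2 per week × 1 week = 2
- High: 3 per week × 3 weeks = 9

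Of these 2 to 9 results, at most 1 can be counted (as the discontinuation test), and 0 if the abnormality is first found at Visit 9.

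**6. Illustration of one omitted case.** Clopper-Pearson 95% intervals with n = 74, the planned arm size:
- 0/74: upper limit 1 − 0.025^(1/74) = 4.86%, so 0% (0% to 4.9%)
- 1/74 = 1.35%: lower limit 1 − 0.975^(1/74) = 0.03%; upper limit from the beta(2, 73) 97.5% point = 7.30%, so 1.4% (0.03% to 7.3%)

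**The case against.** The strongest reply is that this is a choice between two defensible conventions. Protocol 8.11.3 also summarises scheduled measurements, the liver rows are a SAP addition, and using every result gives closely followed subjects more chances to cross a limit. All of that is true. There is no conflict with the protocol, and the unequal testing has to be disclosed if the rule changes.

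The gap is also narrow. If the trigger sample was scheduled or was the discontinuation test, the subject is already in at least one >3x row. An omission then needs a further limit to be crossed for the first time, at a sample that is neither scheduled nor the discontinuation test. With the taper omitted, only samples after the discontinuation test are lost. This limits how often the problem can arise but does not remove it.

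Other reporting captures much of the clinical content. Criterion b is counted among serious adverse events, and meeting any Appendix 2 criterion makes the event an adverse event. Protocol 8.1 promises subject listings, and the SAP leaves output details to a separate plan that is not available here, so the hepatic form may well be listed. A listing does not correct a tabulated count, however, and for Case 2 the adverse event tables do not show the multiple of ULN.

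Finally, the intervals above are not planned output, no decision rule uses these rows, and the number of repeats does not measure error, since only a new crossing matters. The effect on the difference between arms is not shown. These points stand, and the figures are given as illustration only.

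**Conclusion.** The concern holds. Under SAP 6.3 and 10.3 as written, a liver limit first crossed at an off-schedule repeat is left out of the ever-met rows unless that repeat is recorded as the discontinuation test. This follows from a stated rule, not from a missing detail.

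The number of subjects affected is unknown and may be zero. The direction is certain: the counts can only be understated. For a rare combined enzyme and bilirubin signal, one omitted subject is the difference between one case and none. The primary analysis is untouched, and events that meet criterion b still reach the serious adverse event tables. The change should be made because it is cheap and removes a one-sided undercount in a safety table. The conclusion assumes that Appendix 2 repeats are treated as unscheduled visits, since they appear in neither document's visit schedule.

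**What to change.** Keep every by-visit laboratory summary on scheduled data. Add to SAP 6.3 and to 10.3 item 3:

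> *For the rows that count subjects who ever meet a liver criterion after the first dose, all post-dose results are used, whether scheduled or not, including those held on the hepatic dysfunction follow-up assessment form.*

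Add a footnote to those rows saying that subjects with an abnormal result were tested more often than others.

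The cost is one sentence, one footnote and one extra data source: the follow-up form results, each with the reference range of the laboratory that ran the test. Protocol 9.7.1 already has the sponsor collect site reference values, so multiples of ULN can be derived. Efficacy analyses and by-visit tables do not change. The drawback is unequal test frequency between subjects, which the footnote discloses.
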